1.2.1.5 Study MET56 (Phase III)

MET56 was a Phase III, modified double-blind, randomized, parallel-group, active-controlled, multi-center study to compare the immunogenicity and describe the safety of a booster dose of MenACYW conjugate vaccine to a licensed vaccine in quadrivalent meningococcal conjugate vaccine-primed adolescents (≥ 15 to < 18 years) and adults (≥ 18 years) in the US. Approximately 800 healthy adolescents and adults who had received 1 dose of quadrivalent meningococcal conjugate vaccine 4 to 10 years previously were randomized in a 1:1 ratio to 1 of 2 groups: Group 1 MenACYW conjugate vaccine or Group 2 Menactra[®].

Immunogenicity

MenACYW conjugate vaccine immune responses evaluated by hSBA and rSBA were generally comparable to Menactra[®] immune responses when given as a booster dose.

At D30, MenACYW conjugate vaccine was non-inferior to Menactra[®] for all 4 serogroups as measured by hSBA vaccine seroresponse.

At D06, the differences of the percentages of subjects achieving hSBA vaccine seroresponse between the MenACYW conjugate vaccine group and the Menactra[®] group were > 0 for serogroups A, Y, and W (6.6%, 7.0%, and 10.7%, respectively) and were < 0 for serogroup C (-3.5%), with overlapping 95% CIs.

At D30, the Group 1 / Group 2 hSBA GMT ratio ranged from 1.68 to 4.37 for all serogroups. At D30, meningococcal rSBA GMTs for all serogroups were higher after MenACYW conjugate vaccine than after Menactra[®] for all serogroups. The percentages of subjects with an rSBA vaccine seroresponse after vaccination with MenACYW conjugate vaccine were numerically higher than or comparable to the percentages after Menactra[®].

MenACYW conjugate vaccine was comparable to Menactra[®] when immune response data was analyzed by age, time since first meningococcal vaccination, and quadrivalent meningococcal conjugate vaccine used for priming.

Safety

Overall, vaccination with a booster dose of MenACYW conjugate vaccine in quadrivalent meningococcal conjugate vaccine-primed adolescents and adults aged at least 15 years was found to be safe, with no safety concerns identified.

The safety profile of MenACYW conjugate vaccine was comparable to that of the licensed vaccine, Menactra[®].

No new clinically important findings were identified with administration of a booster dose of MenACYW conjugate vaccine.

1.3 Potential Benefits and Risks

1.3.1 Potential Benefits to Subjects

MenACYW conjugate vaccine is an investigational vaccine that is undergoing active clinical investigation. There may be no direct benefit from receiving the MenACYW conjugate vaccine. However, based on the data generated from previous studies, the immunogenicity profile of the MenACYW conjugate vaccine in different age groups shows that the majority of subjects developed seroprotective levels of antibodies after vaccination. The safety evaluation indicates that the vaccine is well tolerated, and no safety issues have been detected to date. In all, the data support further evaluation of the MenACYW conjugate vaccine in humans.

Subjects who receive Menactra[®] or Quadri Meningo[™] (or any licensed meningococcal vaccine) will likely be protected against meningococcal disease caused by *N. meningitidis* serogroups A, C, Y, and W.

As with any vaccine, MenACYW conjugate vaccine, Menactra[®], or Quadri Meningo[™] (or any licensed meningococcal vaccine) may not protect 100% of individuals against the diseases they are designed to prevent.

1.3.2 Potential Risks to Subjects

Like other vaccines, MenACYW conjugate vaccine, Menactra[®], and Quadri Meningo[™] (or any licensed meningococcal vaccine) may cause injection site reactions such as pain, swelling, and erythema, or certain systemic events such as fever, headache, malaise, and myalgia when administered to children, adolescents, or adults. Other common reactions following the administration of Menactra[®] in children 2 to 10 years of age also include induration at the injection site, irritability, diarrhea, and drowsiness. Common reactions following the administration of Menactra[®] in adolescents and adults 11 to 55 years of age also include induration at the injection site, fatigue, arthralgia, diarrhea, and loss of appetite. There may be a rare possibility of an allergic reaction, which could be severe. There may also be a risk of febrile convulsion in some children who experience high fever. There may be other risks for MenACYW conjugate vaccine, Menactra[®], or Quadri Meningo[™] (or any licensed meningococcal vaccine) that are not yet known.

The following additional adverse events (AEs) have been very rarely reported during post-approval use of Menactra[®]: Guillain-Barré syndrome (GBS), transverse myelitis, acute disseminated encephalomyelitis, vasovagal syncope, facial palsy, dizziness, paraesthesia, convulsion, lymphadenopathy, extensive limb swelling, and hypersensitivity reactions such as anaphylactic / anaphylactoid reaction, wheezing, difficulty breathing, upper airway swelling, urticaria, erythema, pruritus, and hypotension. Because these events were reported voluntarily from a population of uncertain size, it is not possible to reliably estimate their frequency or to establish a causal relationship to Menactra[®] exposure.

GBS has been reported mostly in persons aged 11 to 19 years who had symptom onset within 6 weeks of administration of Menactra[®] (32). A retrospective cohort study carried out in the US using healthcare claims data found no evidence of increased GBS risk associated with the use of that vaccine. The study was able to exclude all but relatively small incremental risks (33).

1.4 Rationale for the Study

The MenACYW conjugate vaccine is designed for the immunization of individuals of all ages (infants 6 weeks of age and older through and including older adults > 56 years of age) against IMD. The purpose of the vaccine is to provide broad coverage against circulating meningococcal strains from serogroups A, C, Y, and W. Compared to a previous Sanofi Pasteur meningococcal conjugate vaccine, Menactra[®], the MenACYW conjugate vaccine is prepared using tetanus toxoid as the carrier protein. Conjugation of polysaccharide antigens to a protein carrier can induce T cell-dependent immune responses, which are anticipated to give rise to higher antibody titers, longer duration of the immune response, and enhanced immunologic memory that allows for a booster response. The program targets licensure of the MenACYW conjugate vaccine in many countries in North America, Europe, Latin America, Africa, the Middle East, and Asia Pacific.

The MenACYW conjugate vaccine is designed to cover broader age groups than those covered by Menomune[®] -A/C/Y/W-135 and Menactra[®]. Menactra[®] has been very successful since its

licensure in 2005; however, it is not licensed in Europe and is not indicated in persons 8 months of age or younger or 56 years of age and older. While Menomune[®] -A/C/Y/W-135 and Menactra[®] are currently licensed in different parts of the world, the MenACYW conjugate vaccine is being developed by Sanofi Pasteur to ultimately replace Menomune[®] -A/C/Y/W-135 and Menactra[®] in the global market as a quadrivalent meningococcal conjugate vaccine indicated in infants/toddlers, children, adolescents, adults, and older adults ≥ 56 years of age. Meningococcal polysaccharide vaccines have 2 important limitations: a) the antibody response is age-dependent, with infants giving the poorest response; and b) polysaccharides alone are T-cell independent immunogens, and therefore no anamnestic response is seen. The immunogenicity of polysaccharide vaccines in infants and children has been shown to be improved by conjugating the polysaccharides to protein carriers. Among the key advantages expected of the tetanus carrier is improved immunogenicity in infants and older adults. Pre-clinical studies using a mouse model and investigating different carriers, showed significant levels of polysaccharide-specific total immunoglobulin G (IgG) and bactericidal responses in response to the formulations with tetanus toxoid as a carrier. Early Phase I/II studies including those with the final formulation (MET39 and MET44) and the recent Phase III studies showed the potential of the candidate vaccine as a very good immunogen in all age groups, including young infants and older adults. The MenACYW conjugate vaccine was found to be immunogenic and well tolerated; it did not raise any safety concerns in the above studies using the final formulation or in the earlier studies.

The purpose of the MET55 study is to compare and describe the immunogenicity and safety of MenACYW conjugate vaccine when administered as a single dose in healthy adults, adolescents, and children in India and healthy adolescents and children in the RSA.

2 Study Objectives

2.1 Primary Objective

To demonstrate the non-inferiority of immunogenicity of a single dose of MenACYW conjugate vaccine compared to Menactra[®] in adolescents and children aged 2 to 17 years in terms of serum bactericidal assay using human complement (hSBA) titers.

The endpoint for the primary objective is presented in Section 9.1.1.1.

2.2 Secondary Objectives

- 1) To describe the antibody titers to the meningococcal serogroups A, C, Y, and W before and at D30 (+14 days) after vaccination with MenACYW conjugate vaccine or Menactra[®] in adults aged 18 to 55 years in India
- 2) To describe the antibody titers to the meningococcal serogroups A, C, Y, and W before and at D30 (+14 days) after vaccination with MenACYW conjugate vaccine or Quadri Meningo[™] (or any locally available licensed meningococcal vaccine) in adults aged ≥ 56 years in India

- 3) To describe the antibody titers to the meningococcal serogroups A, C, Y, and W before and at D30 (+14 days) after vaccination with MenACYW conjugate vaccine or Menactra[®] in children and adolescents aged 2 to 17 years in India and RSA
- 4) To describe the antibody titers to the meningococcal serogroups A, C, Y, and W before and at D30 (+14 days) after vaccination with MenACYW conjugate vaccine or Menactra[®] in children and adolescents aged 2 to 17 years in India
- 5) To describe the antibody titers to the meningococcal serogroups A, C, Y, and W before and at D30 (+14 days) after vaccination with MenACYW conjugate vaccine or Menactra[®] in children and adolescents aged 2 to 17 years in RSA

The endpoints for the secondary objectives are presented in Section 9.2.1.1.

2.3 Observational Objectives

Immunogenicity

- 1) To describe the antibody titers to the meningococcal serogroups A, C, Y, and W before and at D30 (+14 days) after vaccination with MenACYW conjugate vaccine or Menactra[®] in the children and adolescents aged 2 to 17 years by age groups (2 to 9 years of age and 10 to 17 years of age) in India and RSA combined and separated by India only or RSA only

Safety

- 1) To describe the safety profile of MenACYW conjugate vaccine and that of licensed Menactra[®] in adults aged 18 to 55 years in India
- 2) To describe the safety profile of MenACYW conjugate vaccine and that of licensed Quadri Meningo[™] (or any locally available licensed meningococcal vaccine) in adults aged ≥ 56 years in India
- 3) To describe the safety profile of MenACYW conjugate vaccine and that of licensed Menactra[®] in children and adolescents aged 2 to 17 years in India and RSA

The endpoint for the observational objective is presented in Section 9.3.1.1 and the endpoints for the observational safety objectives are presented in Section 9.3.2.2.

3 Investigators and Study Organization

This study will be conducted in approximately 12 sites in India and 7 sites in RSA. Details of the study centers and the Investigators at each center are provided in the “List of Investigators and Centers Involved in the Trial” document.

An internal Safety Management Team (SMT) and an independent Data Safety Monitoring Board (DSMB) will be utilized for this study. The DSMB committee will assess the progress of the clinical study and the safety data, and recommend to Sanofi Pasteur whether to continue, modify, or stop the study. The DSMB will be responsible for the evaluation of the safety of MenACYW conjugate vaccine and for making recommendations to the Sponsor on a medical and ethical basis. A formal DSMB review is proposed after capturing 7 days of safety information from a subset

(100 subjects across both cohorts) of subjects of the Adult Cohorts Ia and Ib before the enrollment of the children and adolescents in Cohort II for India only. A DSMB charter will be developed before study start.

The Sponsor's Responsible Medical Officer (the RMO, the person authorized to sign this protocol and any amendments on behalf of the Sponsor) is [REDACTED], MD, Clinical Team Leader (CTL).

4 Independent Ethics Committee / Institutional Review Board

Before the investigational product can be shipped to the investigational site and before the inclusion of the first subject, this protocol, the Informed Consent Forms (ICFs), and the Assent Form, subject recruitment procedures, and any other written information to be provided to subjects must be approved by, and / or receive favorable opinion from, the appropriate Independent Ethics Committees (IECs) or Institutional Review Boards (IRBs).

In accordance with Good Clinical Practice (GCP) and local regulations, each Investigator and / or the Sponsor are responsible for obtaining this approval and / or favorable opinion before the start of the study. If the protocol is subsequently amended, approval must be re-obtained for each substantial amendment. Copies of these approvals, along with information on the type, version number, and date of document, and the date of approval, must be forwarded by the Investigator to the Sponsor together with the composition of the IEC / IRB (the names and qualifications of the members attending and voting at the meetings).

The Investigator or Sponsor will submit written summaries of the status of the study to the IEC / IRB annually, or more frequently if requested. All SAEs occurring during the study will be reported by the Investigator to the IEC / IRB, according to the IEC / IRB policy.

5 Investigational Plan

5.1 Description of the Overall Study Design and Plan

5.1.1 Study Design

This study will be a Phase III, modified double-blind, randomized, parallel-group, active-controlled, step-wise, multi-center study to compare and describe the immunogenicity and safety of MenACYW conjugate vaccine when administered as a single dose in healthy adults, adolescents and children in India and a modified double-blind, randomized, parallel-group, active-controlled, multi-center study to compare and describe the immunogenicity and safety on MenACYW conjugate vaccine when administered a single dose in healthy adolescents and children in RSA.

5.1.2 Justification of the Study Design

The purpose of MET55 will be to support licensing of MenACYW conjugate vaccine in India and RSA.

This study will be conducted to evaluate and/or describe the immunogenicity and describe the safety of MenACYW conjugate vaccine in children, adolescents, and adults. The primary aim of the study is to compare the immunogenicity responses obtained after MenACYW conjugate vaccine administration to the responses obtained after the administration of a licensed meningococcal vaccine, Menactra[®] in children and adolescents. This study will also generate descriptive immunogenicity data from the adult population (18 years of age and above) for MenACYW conjugate vaccine. The safety of the MenACYW conjugate vaccine will be described in the whole study population. Since MenACYW conjugate vaccine has been evaluated in children, adolescents, and adults in many countries without raising any safety concerns, safety assessments will be done up to 30 days after vaccination.

The study has different cohorts according to age and different comparators according to their licensure status in India; hence the study has a modified double-blind design. Only the pharmacist / vaccination study staff in charge of handling the study product will be aware of the type of product administered, whereas the physician and other study staff will remain blinded to the subjects' group allocations throughout the study until the final clinical study report is available. Since the primary objective of this study has a serological endpoint, the laboratory technicians will also remain blinded to the subjects' group allocations throughout the study up to the database lock to avoid any bias.

For ages 2 to 55 years, Menactra[®] has been chosen as a comparator as it is the licensed meningococcal conjugate vaccine in this age group in India. For ages 56 years and above, Quadri Meningo[™] has been chosen as a comparator as this is a vaccine licensed and currently available in the market in India for this age group. However, any locally available licensed meningococcal vaccine will be used as comparator in case Quadri Meningo[™] is not available in the Indian market at the time of the study.

MET55 will use a step-wise enrollment only in India. The older populations (adults; ie, Cohorts Ia and Ib) will be recruited before initiating the study in children and adolescents younger than 17 years of age (ie, Cohort II).

A DSMB will be used in this study. The DSMB will be involved in reviewing any life-threatening or fatal SAE cases considered as being related to vaccine throughout the study. Additionally, the study will be monitored by the DSMB, as they will be the only group with access to the unblinded data for the Early Safety Data Review (ESDR) that will take place prior to enrolling Cohort II in India. The DSMB will review the unblinded data and advise to either continue the study as planned or to stop the study. The procedures governing the function of the DSMB are outlined in the DSMB charter.

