12.5 Determination of Sample Size and Power Calculation

Calculation of Sample Size:

Approximately 1332 subjects will be enrolled. An estimated 15% drop-out rate (only ages 2 - 17 years) from enrollment will result in approximately 1190 subjects in the per-protocol population available for immunogenicity analyses.

For the Primary Objective

With 396 evaluable subjects in the combined group (Gr5 + Gr7) and 396 evaluable subjects in the combined group (Gr6 + Gr8), the study will have 90% power using Farrington and Manning's method to declare the non-inferiority of the combined group (Gr5+ Gr7) versus the combined group (Gr6 + Gr8) based on A, C, Y, W antibodies in adolescents and children aged 2 to 17 years (assuming 15% drop-out rate for each group). The power is calculated with the assumption that the estimate from the investigational group equals that of the control group.

Table 12.1: Power of the study based on the primary objective of non-inferiority in children and adolescents aged 2 to 17 years

| Antigen | Estimated* MenACYW | Estimated Menactra® | Non-inferiority | Power |
|----------------|-----------------------|------------------------|-----------------|---------|
| A | 76% | 76% | 10% | 91% |
| C | 94.5% | 94.5% | 10% | > 99.9% |
| Y | 89% | 89% | 10% | > 99.9% |
| W | 95% | 95% | 10% | > 99.2% |
| Overall | | | | 90% |

Note: Evaluable subjects:

Combined group (Gr5 + Gr7) = 396 subjects

Combined group (Gr 6 + Gr8) = 396 subjects

Since the hypothesis needs to be met for all serogroups, no alpha adjustment for multiple comparisons is necessary in these calculations.

* Estimated seroresponses are based on the results of a study (50) conducted in India in subjects aged 2 to 75 years. The estimates were the average of overall rates of 2 age groups (2 to 10 years and 11 to 18 years). Borrow et al. reported that incidence rates vary in RSA by province but are currently low overall (0.36/100 000 in 2014) with the majority of disease caused by MenW, followed by MenB. Approximately 66-77% of disease is caused by MenA, C, Y, or W. Due to any lack of published data from RSA it is assumed that the response in subjects aged 2-17 years will be similar between India and RSA. Additionally, any variability should balance itself out due to the wider age range.

13 Ethical and Legal Issues and Investigator / Sponsor Responsibilities

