5.1 Statistical Methods

5.1.1 Hypotheses and Statistical Methods for Primary Objective(s)

5.1.1.1 Hypotheses

Thirty days after the administration of MenACYW conjugate vaccine or Menactra[®], the percentages of subjects who achieve ≥ 1:8 in hSBA titers for meningococcal serogroups A, C, Y,

and W in the combined group (Group 5 + Group 7) are non-inferior to the corresponding percentages in the combined group (Group 6 + Group 8)

Null hypothesis (H0): $p(G5 + G7) - p(G6 + 8) \le -10\%$

Alternative hypothesis (H1): p(G5 + G7) - p(G6 + G8) > -10%

where p(G5 + G7) and p(G6 + G8) are the percentages of subjects who achieve $\geq 1:8$ in hSBA titers in the combined group (G5 + G7) and the combined groups (G6 + G8), respectively.

Each of the serogroups A, C, Y, and W will be tested separately. If the lower limit of the 2-sided 95% confidence interval (CI) of the difference between the 2 proportions is > -10%, the inferiority assumption will be rejected.

For the 4 non-inferiority hypotheses, the CI of the difference in proportions will be computed using the Wilson score method without continuity correction (2). The overall non-inferiority of this objective will be demonstrated if all 4 individual null hypotheses are rejected.

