5.1.1.2 Statistical Methods

Each of the serogroups A, C, W, and Y will be tested separately. If the lower limit of the 2-sided 95% CI of the difference between the 2 proportions is > -10%, the inferiority assumption will be rejected. For the 4 non-inferiority hypotheses using the vaccine seroprotection rates, the 95% CI of the difference in proportions between (Group 5 + Group 7) and (Group 6 + Group 8) will be computed using the Wilson Score method without continuity correction (2).

Let $\hat{\theta} = p_1 - p_2$, then $L = \hat{\theta} - \delta$ and $U = \hat{\theta} + \varepsilon$ are respectively the lower and the upper limits of the CI, where:

$$\delta = Z_{0.025} \sqrt{\left\{ \frac{l_1(1-l_1)}{n_1} + \frac{u_2(1-u_2)}{n_2} \right\}}$$

$$\varepsilon = Z_{0.025} \sqrt{\left\{ \frac{l_2(1 - l_2)}{n_2} + \frac{u_1(1 - u_1)}{n_1} \right\}}$$

l₁ and u₁ are calculated from the CI of the single proportion in Group 1 given by:

$$\frac{(2n_1p_1 + Z_{0.025}^2 \pm Z_{0.025}\sqrt{(Z_{0.025}^2 + 4n_1p_1(1-p_1))})}{2(n_1 + Z_{0.025}^2)}$$

l₂ and u₂ are calculated from the CI of the single proportion in Group 2 given by:

$$\frac{(2n_2p_2 + Z_{0.025}^2 \pm Z_{0.025}\sqrt{(Z_{0.025}^2 + 4n_2p_2(1-p_2))})}{2(n_2 + Z_{0.025}^2)}$$

where $Z_{0.025}$ is the upper 97.5th percentile of the standard normal distribution.

The overall non-inferiority of this objective will be demonstrated if all 4 individual null hypotheses are rejected.

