5.1.2.2 Statistical Methods

Immunogenicity

Secondary Objectives 1 and 2:

Descriptive statistics will be provided for the antibody titers against meningococcal serogroups contained in MenACYW conjugate vaccine and Menactra[®] in adults aged 18 to 55 years (Group 1 versus Group 2) or Quadri MeningoTM (or any locally available licensed meningococcal vaccine) in adults aged \geq 56 years (Group 3 versus Group 4) in India.

Secondary Objectives 3, 4, and 5:

Descriptive statistics will be provided for the antibody titers against meningococcal serogroups contained in MenACYW conjugate vaccine and Menactra[®] in adolescents and children aged 2 to 17 years in India and RSA combined ([Group 5 + Group 7] versus [Group 6 + Group 8]), India only (Group 5 versus Group 6), and RSA only (Group 7 versus Group 8).

In general, categorical variables in Cohorts Ia and Ib (in India), II (in India and RSA) will be summarized and presented by frequency counts, percentages, and CIs. The 95% CIs of point estimates will be calculated using the normal approximation for quantitative data and the exact binomial distribution (Clopper-Pearson method) (1) for percentages.

Descriptive analyses on A, C, Y, and W serogroups on D0 and D30 (+14 days) using hSBA and rSBA (in a subset)^b will be generated as follows:

Descriptive analyses of hSBA include but will not be limited to:

- Geometric mean titers (GMTs) and 95% CI
- Titer distribution and reverse cumulative distribution curves (RCDCs)
- Percentage of subjects with titer $\geq 1:4$ and $\geq 1:8$ and 95% CI

• Groups 5, 6, 7, and 8: 100 subjects each

·

Note: rSBA data will be generated in a subset of subjects as follows:

[•] Groups 1, 2, 3, and 4: 50 subjects each

- Percentage of subjects with titer ≥ 4-fold rise from pre-vaccination to post-vaccination, and 95% CI
- Percentage of subjects with hSBA vaccine seroresponse^c and 95% CI

Descriptive analyses of rSBA (in a subset) will include but not be limited to:

- GMTs and 95% CI in a subset of age groups
- Titer distribution and RCDCs
- Percentage of subjects with titer ≥ 1.8 and ≥ 1.128 and 95% CI
- Percentage of subjects with titer ≥ 4-fold rise from pre-vaccination to post-vaccination, and 95% CI
- Percentage of subjects with rSBA vaccine seroresponse^d and 95% CI in a subset of age groups

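### The trial supports licensure in two countries, but the only vaccine difference with a confidence interval is pooled; India and RSA get single-arm intervals only

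*Protocol*

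**What the plan says.** The purpose in Protocol 5.1.2 is two-country: "The purpose of MET55 will be to support licensing of MenACYW conjugate vaccine in India and RSA". Protocol 5.1.3 and 6.5 randomise 1:1 within each country, Group 5 against 6 in India and Group 7 against 8 in RSA.

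The primary hypothesis is pooled. SAP 5.1.1.1 rejects inferiority for a serogroup "If the lower limit of the 2-sided 95% confidence interval (CI) of the difference between the 2 proportions is > -10" per cent. SAP 5.1.1.2 gives the formula for "the 95% CI of the difference in proportions between (Group 5 + Group 7) and (Group 6 + Group 8"). No other difference between vaccines is given an interval.

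Secondary objectives 4 and 5 are country-specific. SAP 5.1.2.2 names the comparisons "India only (Group 5 versus Group 6), and RSA only (Group 7 versus Group 8"). The outputs listed there are GMTs, titre distributions, percentages at or above 1:4 and 1:8, four-fold rise and seroresponse. Their intervals belong to single estimates: Clopper-Pearson for percentages, normal approximation for quantitative data. Protocol 12.1.2.2 says the same, and both documents state that no hypotheses are tested on these objectives.

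The footnote to the power table in Protocol 12.5 notes the lack of published RSA data, says that "it is assumed that the response in subjects aged 2-17 years will be similar between India and RSA", and adds that "any variability should balance itself out due to the wider age range".

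**The concern.** Each country is a complete randomised comparison, so the vaccine difference within it can be estimated without bias. The plan labels these comparisons as one group versus another but stops at single-arm summaries. Whether two single-arm intervals overlap does not tell a reader how uncertain the difference is.

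There are reasons to look by country. RSA subjects enter whatever their HIV result (Protocol 5.2.5), and similarity of response is assumed rather than known. A wider age range does not cancel a country difference, because both countries enrol the same ages with the same age strata. If MenACYW fell short in one country, the pooled criterion could still be met, and the tables for that country would show two percentages without the precision of the gap between them.

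**Working it through.** **Inputs.** Margin -10 points, two-sided 95% interval (SAP 5.1.1.1). Protocol 12.5: "With 396 evaluable subjects in the combined group (Gr5 + Gr7) and 396 evaluable subjects in the combined group (Gr6 + Gr8"), 15% drop-out, and common rates of A 76%, C 94.5%, Y 89%, W 95%. Per country and arm, 396/2 = 198 evaluable, which agrees with 233 × 0.85 = 198.

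**Reproducing the plan.** Farrington-Manning power, n = 396 per arm, true difference 0, one-sided 0.025:
- Hand check for A with unpooled variance: SE = √(2 × 0.76 × 0.24/396) = 0.03035; 0.10/0.03035 - 1.96 = 1.335; power 90.9%.
- Farrington-Manning: A 90.8% (stated 91%), C 99.99%, Y 99.25%, W 99.998%; product 90.1% (stated 90%).
- The stated Y and W entries look interchanged; overall power is unaffected.
- Enrolment: 396/0.85 = 466 per pooled arm, as planned.

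**A shortfall in one country.** The documents give no country-specific rates, so the scenario is an assumption: true difference 0 in India and -12 in RSA for one serogroup. I used 400,000 simulated trials with the SAP's Wilson interval.

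| Menactra rate | Pooled criterion passes | RSA alone would pass |
|---|---|---|
| 76% | 25% | 0.9% |
| 89% | 37% | 0.6% |
| 94.5% | 51% | 0.5% |

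Hand check at 76%: the true pooled difference is (0 - 12)/2 = -6. SE = √[(198 × 0.76 × 0.24 + 198 × 0.64 × 0.36)/396² + 0.76 × 0.24/396] = 0.0313. Then (0.10 - 0.06)/0.0313 - 1.96 = -0.68, a pass probability of 25%.

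The range by size of the RSA shortfall, at the same three rates:
- -10 points: 36%, 54%, 72%
- -15 points: 12%, 17%, 22%

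**All four serogroups.** At zero difference the other serogroups pass with probability 0.911 (A), 0.993 (Y) and about 1 (C, W). With independence assumed, overall success with a single -12 shortfall is:
- in A: 0.249 × 0.993 = 25%
- in Y: 0.367 × 0.911 = 33%
- in C: 0.506 × 0.911 × 0.993 = 46%

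If RSA were 12 points lower on all four: 0.249 × 0.367 × 0.506 × 0.526 = 2%. At 10 points lower on all four: 0.363 × 0.537 × 0.716 × 0.740 = 10%.

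**Worked counts (assumed).** India 188/198 v 188/198; RSA 164/198 v 188/198.
- Pooled: 352/396 v 376/396, difference -6.06. With l₁ = 0.8541 and u₂ = 0.9671, δ = 1.96 × √(0.8541 × 0.1459/396 + 0.9671 × 0.0329/396) = 3.90 points. The interval is -9.96 to -2.28, which passes.
- RSA: difference -12.12, interval -18.42 to -6.02.
- The planned tables would show RSA as 82.8% (76.8 to 87.8) and 94.9% (90.9 to 97.6).

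**Why two single-arm intervals are not enough.** Assumed counts 128/198 v 150/198 have exact intervals 57.6 to 71.3 and 69.2 to 81.6, which overlap. The Wilson interval for the difference is -11.1 (-19.9 to -2.1), which excludes zero.

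**What a country interval can and cannot do.** Half-width at zero difference is about 1.96 × √(2p(1-p)/198): 8.4 points at 76%, 6.2 at 89%, 4.5 at 94.5%. That is informative as an estimate. Within-country power against -10 points is A 64%, Y 87%, C 98%, W 98.5%; the product is about 54%. The difference between the two country effects has half-width √2 times larger: about 11.9 points at 76% and 8.7 at 89%.

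**The case against.** The strongest reply is that the country results are already planned. The percentage at or above 1:8, which is the primary measure, is reported with an exact interval for each vaccine within India and within RSA, and again by age group. A reader might infer from the pooled test that a shortfall in one country would leave no trace. The documents do not support that: in the worked example the planned table shows 82.8% against 94.9%. This part of the reply stands, and what is missing is only the interval for the difference.

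Second, a reader might call the pooled pass a false positive. It is not. The hypothesis concerns the combined groups, and with 0 and -12 the true pooled difference is -6, inside the margin.

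Third, a reader might take the footnote as assuming equal vaccine effects in the two countries. It says similar responses, and it supports the planning rates in the power table, not the choice to pool.

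Fourth, step-wise enrolment in India is a safety gate and gives no reason for a different vaccine difference. HIV status in RSA is already a conditional subgroup in SAP 5.1.4.1. Both points are fair.

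Finally, the output lists are described as not exhaustive, so the difference could be added later. That does not prespecify it, and a country difference produced only after a disappointing result carries less weight.

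**Conclusion.** The point holds as a reporting gap. For a trial supporting two licensures, neither country has a prespecified vaccine difference with its uncertainty. A -12 point shortfall in RSA for one serogroup would pass that serogroup's pooled criterion about 25% to 51% of the time, against under 1% for RSA alone. These figures rest on an assumed country split, 198 evaluable per arm per country, and Menactra rates of 76% to 94.5% taken as equal in both countries. They fall quickly if the shortfall is larger or covers several serogroups. The primary test is valid as written, and nothing here calls for country-level non-inferiority tests, for which the trial is not sized.

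**What to change.** In SAP 5.1.2.2, under secondary objectives 4 and 5, add for each serogroup the Group 5 minus Group 6 and Group 7 minus Group 8 differences in the percentage with hSBA at or above 1:8, and in hSBA seroresponse. Use the Wilson score 95% interval of SAP 5.1.1.2 and label the results descriptive.

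The difference between the two country effects may be shown with its interval, also descriptive, with a note that it is imprecise and that the trial is not sized to show consistency or country-level non-inferiority.

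The cost is one more table from existing data and an existing formula. No alpha is spent and no subjects are added. The downside is that a noisy country estimate may need explaining. Rewording the footnote about variability balancing out is optional and changes no result.
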